6.1 Study treatment

The sponsor will provide the open-label study medication oral deferasirox FCT tablets: 90 mg, 180 mg and 360 mg. The control arm will undergo phlebotomy at intervals determined by the treating physician's clinical assessment for optimal iron control.

6.1.1 Dosing regimen

Study treatments	Pharmaceutical form and route of administration	Dose	Frequency and/or Regimen
Deferasirox FCT	Tablet for oral use	7 mg/kg (Initial dose)	Daily
Phlebotomy	Venipuncture	NA	determined by PI

Table 6-1 Dose and treatment schedule

After a 4-week screening period, eligible patients will be randomized 2:1 to receive deferasirox FCT or phlebotomy.

Patients randomized to deferasirox FCT will receive 7 mg/kg once daily. The daily dose is calculated based on the patient's weight, then rounded up or down to the nearest whole tablet according to the available strengths of deferasirox FCT tablets (90 mg, 180 mg, and 360 mg; see Appendix 14.1). After 3 months (12 weeks), adjust dose as needed based on SF levels listed below with the maximum dose adjustment of 3.5 mg/kg/day per month.

- SF < $300 \mu g/L$ Decrease to 3.5 mg/kg/day
- SF 300-1000 µg/L Maintain 7 mg/kg/day
- SF > 1000-2000 μ g/L Increase to 10.5 mg/kg/day
- SF > 2000 μ g/L Increase to 14 mg/kg/day

When SF reaches the study target $\leq 100 \ \mu g/L$, deferasirox FCT must be interrupted and the patient enters the maintenance phase.

During the maintenance phase, when SF \geq 300 µg/L, deferasirox FCT 3.5 mg/kg/day may be re-initiated. If deferasirox FCT 3.5 mg/kg/day is not controlling SF and it continues to increase, increase to a maximum 7 mg/kg/day. Treat until the SF reaches \leq 100 µg/L, then interrupt treatment again.

During regular study visits, the investigator or pharmacist will dispense the appropriate number of deferasirox FCT tablets to each patient. The number of tablets of each strength dispensed will be recorded in the study Drug Dosing Log. Each time deferasirox FCT is dispensed, the investigator must provide detailed instructions to patients, instruct them to take the assigned amount of study drug, and return all unused study medication every 4 weeks. Returned study medication must be counted and recorded. The field monitor must note the drug accountability during site visits and at the completion of the trial.

Medication labels must be in the local language and comply with the legal requirements of the countries where the study is implemented. Labels will have study identifier and storage conditions for the study drug, but no patient information.

Patients should swallow the required number of deferasirox FCT, with or without a light meal, and around the same time each day.

Patients should not make up missed doses. A missed dose is when the full dose is not taken within 8 hours of the usual time of the daily dose. Omit that day's dose, and resume with the next scheduled dose.

Dose adjustments for safety are allowed at any time and must be in increments or decrements of 3.5 or 7 mg/kg/day. For this study, the maximum dose of deferasirox FCT is 14 mg/kg/day.

Patients randomized to phlebotomy will receive treatment at a frequency determined by the treating physician's judgment for optimal iron control. Phlebotomy must be interrupted when a patient achieves the target SF $\leq 100 \ \mu$ g/L. Treatment may be re-initiated when SF $> 100 \ \mu$ g/L.

Patients randomized to deferasirox FCT are not allowed to receive phlebotomy during the study treatment.

Patients randomized to the deferasirox FCT arm who discontinued from treatment may receive phlebotomy during Post-treatment Ocular Follow-up at a frequency determined by the physician.

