6.3 Dose modifications

6.3.1 Dose modification and dose delay

For patients who do not tolerate the protocol-specified dosing schedule, dose interruptions and/or reductions are either recommended or mandated in order to allow patients to continue the study treatment of defension FCT.

These dose modifications are summarized in Table 6-2. Deviations from the mandatory dose interruptions and/or reductions are not allowed. Permanent treatment discontinuation of deferasirox FCT is mandatory for specific events indicated in Table 6-2 or listed in Section 7.1.5.

These dose changes must be recorded on the Dosage Administration Record eCRF. It is important to keep an accurate dose adjustment records to enable an adequate evaluation of exposure.

Phlebotomy will be conducted at a frequency determined by the treating physician's clinical judgement for optimal iron control. The name of the facility, the date of phlebotomy, hematocrit level prior to phlebotomy and amount of blood withdrawn must be captured in Phlebotomy Record and local lab eCRFs. Phlebotomy must be interrupted when SF $\leq 100 \mu g/L$ and may be resumed when SF $\geq 100 \mu g/L$.

Novartis Amended Protocol Version 01 (Clean)

Table 6-2 Criteria for dose reduction / interruption and re-initiation of deferasirox FCT

Dose modifications for ICL670F2203		
Serum Ferritin (SF)		
After an initial starting dose (7 mg/kg/day) for 3 months (12 weeks), dose may be adjusted based on SF level. Dose increase cannot be more than 3.5 mg/kg/day at each adjustment.		
<300 µg/L	Decrease to 3.5 mg/kg/day	
300-1000 μg/L	Maintain 7 mg/kg/day	
>1000-2000 µg/L	Increase to 10.5 mg/kg/day	
>2000 µg/L	Increase to 14 mg/kg/day (higher doses are not allowed.)	
SF ≤ 100 μg/L at any time	Interrupt deferasirox FCT	
SF \geq 300 µg/L after dose interruption	Re-initiate deferasirox FCT 3.5 mg/kg/day. If SF continues to increase, increase to 7 mg/kg/day (maximum dose for maintenance phase).	
Body Weight		
Increase/decrease if weight changes >10% compared to baseline weight or weight at last dose adjustment due to a change in weight	Dose of study medication will be adapted using Dosing Table (provided in Appendix 14.1) When weight changes >10% compared to baseline weight or weight at last dose adjustment due to a change in weight, re-calculate dose. Smaller variations in weight (<10%) do not require dose adjustments.	
Investigations (Renal)		
Serum creatinine		
Single increase	Maintain dose and repeat assessment at next visit.	

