Increased creatinine ≥ 33% from baseline (average of 2 samples) resulting in creatinine > ULN x 2 consecutive samples (at least 2 weeks apart)	Decrease by 7 mg/kg/day or interrupt if already at 7 mg/kg/day or lower.	
If dose is decreased, but increasing creatinine > ULN	Interrupt treatment.	
After interruption, if creatinine returns to within normal limits on 2 consecutive visits.	Resume 50% of the most recent dose prior to interruption. If after another 4 weeks, creatinine remains stable, resume 100% dose (adjust for weight if needed).	
Creatinine clearance > 40 and < 60 mL/min	Caution in patients if there are additional risk factors that may impair renal function, such as concomitant medications, dehydration, or severe infection.	

Dece medifications for ICL 67052202	
Creatinine clearance < 40 mL/min	Deferasirox must be discontinued.
or increased serum creatinine > 2x age-appropriate ULN	
Urine protein/creatinine ratio	
Any proteinuria	If new or worsening pre-existing proteinuria (assessed by dipstick), collect a urine sample for assessment by the central/local laboratory.
	In case of a single increase of the urinary protein/creatinine ratio, repeat the assessment at the next visit.
> 0.5 urine protein/ creatinine ratio (mg/mg) in two consecutive non-first void urine samples (a minimum of 48h apart), if all other causes of proteinuria have been	Decrease deferasirox by 50%. If UPCR resolves (< 0.5mg/mg) at the next study visit, resume 100% dose.
excluded.	
> 1.0 (mg/mg) in two consecutive non-first void urine	Interrupt deferasirox FCT.
samples (a minimum of 48h apart)	If the increased UPCR resolves (< 0.5 mg/mg) at the next study visit, resume dose at 50% of the last dose. If UPCR remains within normal limits after 4 weeks at the 50% reduced dose, resume study medication at 100% of the last dose.
Persistent proteinuria	If proteinuria persists, discontinue study treatment if the investigator believes it is in the best interest of the patient.
	Novartis may be contacted by the investigator to discuss dosing options.
	Dose adjustment must be based on central/local laboratory results.
Investigations (Hepatic)	
Isolated direct (conjugated) Bilirubin elevation	
> ULN – 1.5 x ULN	Maintain dose
> 1.5 - 3.0 x ULN	Interrupt dosing. Monitor LFTs ^a weekly or more frequently if clinically indicated until resolved to \leq 1.5 x ULN: If resolved \leq 14 days, then maintain dose.
	If resolved > 14 days, then \downarrow 1 dose level (3.5 mg/kg/day FCT)

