Combined ^b AST or ALT and total bilirubin elevations	
Normal baseline ALT and AST and total bilirubin:	
AST or ALT > 3.0 x ULN with total bilirubin > 2.0 x ULN without evidence of cholestasis ^c OR	Permanently discontinue deferasirox.

Novartis	
Amended Protocol Version 01 (Clean))

Dose modifications for ICL670F2203		
In patients with elevated baseline AST or ALT or total bilirubin:	Repeat as soon as possible, preferably within 48 hours from awareness of abnormal results. Monitor LFTs ^a weekly or more frequently if clinically indicated until AST, ALT, or bilirubin resolve to baseline or stabilize	
[AST or ALT > 2x baseline AND > 3.0 x ULN] OR	over 4 weeks. Refer to Section 6.3.3.1 for additional follow-up evaluations as applicable.	
[AST or ALT > 8.0 x ULN], combined with [total bilirubin > 2x baseline AND > 2.0 x ULN]		
Hepatic Impairment		
Moderate hepatic impairment (Child-Pugh Class B)	Interrupt deferasirox and monitor patient. If liver disease prognosis improves, re-start deferasirox 7 mg/kg/day FCT or 50% of previous dose, whichever is less. Increase dose 3.5 mg/kg/day FCT every 2 weeks to a maximum of 50% of previous dose if the investigator determines that the dose increase is in the best interest of the patient.	
Severe hepatic impairment (Child-Pugh Class C)	Discontinue deferasirox.	
Skin and subcutaneous tissue disorders		
Severe skin reaction		
Severe skin reactions, including Stevens-Johnson	Deferasirox must be immediately discontinued and not reintroduced	
syndrome (SJS) and Toxic epidermal necrosis (TEN)		
Drug reaction with eosinophilia and systemic symptoms (DRESS)		
Skin rash (other than SJS)		
Mild/moderate severity (minimal symptoms which require no or minimal supportive treatment)	Continue study drug without dose adjustment. If the rash persists >1 week or becomes more severe, interrupt dosing. After the rash resolves, resume study drug at 50% of last dose. If the rash does not recur, increase dose to	
	100% of dose after 2 weeks.	
Severe rash (distressing symptoms requiring	Interrupt treatment until resolution of rash.	
interruption of study medication and/or systemic steroids)	After the rash resolves, resume at 50% dose. If necessary, a brief course of oral steroids may be given concurrently with resumption of study drug. If the rash does not recur, increase in steps of 3.5 mg/kg/day for deferasirox FCT every 2 weeks until last dose is achieved. If the rash recurs, discontinue study treatment.	
Other adverse events		

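### At 3.5 and 10.5 mg/kg/day the step rule in Protocol 6.1.1 and the 50% decrease for proteinuria in Table 6-2 cannot both be followed, and the severe-rash row is inconsistent with itself at the same two levels

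*Protocol*

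**What the plan says.** Protocol 6.1.1 allows dose changes for safety at any time but says that they "must be in increments or decrements of 3.5 or 7 mg/kg/day". It makes no exception for Table 6-2. The same section sets the dose levels: "Decrease to 3.5 mg/kg/day", "Maintain 7 mg/kg/day" (also the starting dose), "Increase to 10.5 mg/kg/day", and a top level, since "the maximum dose of deferasirox FCT is 14 mg/kg/day". Appendix 14.1 has dosing tables for these four levels only.

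Table 6-2, in Protocol 6.3.1, uses percentages in several rows:

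- **UPCR above 0.5 mg/mg, two consecutive samples:** "Decrease deferasirox by 50" per cent, with return to the full dose if the ratio resolves by the next study visit. There is no interruption first.
- **Severe rash:** interrupt, restart at half dose, then go up by 3.5 mg/kg/day every two weeks to the last dose.
- **Mild or moderate rash that persists or worsens:** interrupt, then "resume study drug at 50% of last dose".
- **Creatinine recovery, and UPCR above 1.0 mg/mg:** interrupt, then restart at half dose.

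Other rows follow the step rule. The direct creatinine reduction is 7 mg/kg/day, and the hepatic reductions are one level of 3.5 mg/kg/day. On the force of the table, 6.3.1 says: "Deviations from the mandatory dose interruptions and/or reductions are not allowed". It also says that modifications may be recommended or mandated, and does not label the rows.

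**The concern.** A halving rule and a fixed-step rule agree only where half the current dose is itself a permitted step. With levels spaced at 3.5 mg/kg/day, that cannot hold at every level. The row for UPCR above 0.5 is the clearest case, because it is a direct reduction of a running dose, which is what the step rule describes.

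What is at stake is consistent safety dosing. Two sites facing the same laboratory result at the same dose could each follow a stated rule and reach different doses, and each would depart from the other rule. The 3.5 mg/kg/day level is part of the planned regimen: it is the dose for serum ferritin below 300 µg/L after week 12, and the re-initiation dose in the maintenance phase.

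**Working it through.** **Inputs.** Permitted steps 3.5 or 7 mg/kg/day and levels D = 3.5, 7, 10.5, 14 (Protocol 6.1.1); 50% rules (Table 6-2); tablet totals in multiples of 90 mg and the nearest-available-dose rule (6.1.1, Appendix 14.1).

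**Step 1: does halving give a permitted step?** Half dose = D/2; step = D − D/2.

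| D | D/2 | Step | Permitted? | Doses that permitted decrements reach |
|---|---|---|---|---|
| 3.5 | 1.75 | 1.75 | no | 0 |
| 7 | 3.5 | 3.5 | yes | 3.5 or 0 |
| 10.5 | 5.25 | 5.25 | no | 7 or 3.5 |
| 14 | 7 | 7 | yes | 10.5 or 7 |

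The rules conflict at two of the four levels. The return to full dose in the UPCR row needs the same unpermitted step upward: 1.75 or 5.25.

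**Step 2: does the severe-rash row return to the last dose?** Start at D/2 and add 3.5 each time.

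- From 7: 3.5, 7. It lands.
- From 14: 7, 10.5, 14. It lands.
- From 3.5: 1.75, 5.25. It overshoots by 1.75.
- From 10.5: 5.25, 8.75, 12.25. It overshoots by 1.75.

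This conflict lies inside one row and does not depend on 6.1.1.

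**Step 3: does tablet rounding remove the conflict?** The appendix tables reproduce: each entry is the nearest multiple of 90 mg to D × weight at every whole-kg weight from 35 to 140 (106 weights). I then halved each table dose, rounded to 90 mg, and asked whether the result can equal the table dose for a permitted target, or zero.

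- From 7 and from 14: 106 of 106 weights.
- From 10.5: 11 of 106.
- From 3.5: 4 of 106 (35–38 kg, where the match is zero dose).

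Rounding half the mg/kg target instead gives 7 of 106 from 10.5 and 0 of 106 from 3.5. Rounding therefore does not generally reconcile the rules. Example at 70 kg on 10.5: the table dose is 720 mg and half is 360 mg, against table doses of 450 mg (level 7) and 270 mg (level 3.5).

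**Step 4: what does the nearest-dose rule give at 3.5 mg/kg/day?** Target = 1.75 × weight.

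- 70 kg: 122.5 mg. The nearest total is 90 mg (32.5 mg away, against 57.5 mg for 180 mg). From 270 mg this is a cut of 180/270 = 67%.
- 80 kg: 140 mg. The nearest total is 180 mg (40 mg away, against 50 mg for 90 mg). From 270 mg this is a cut of 90/270 = 33%.
- 35–38 kg: 61.25 to 66.5 mg. The nearest total is 90 mg, the current dose, so there is no cut.

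Halving the dispensed 270 mg gives 135 mg, exactly midway between 90 and 180 mg, where nearest-dose rounding gives no unique answer.

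**The case against.** The strongest reply is that Table 6-2 is specific and 6.1.1 is general, so sites will follow the table; that most of its 50% rows are restarts from zero rather than adjustments; and that the nearest-dose rule makes a table for 1.75 or 5.25 mg/kg/day unnecessary.

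Much of this stands. The creatinine, UPCR above 1.0 and mild/moderate rash rows are restarts after interruption, and it is arguable whether a rule on increments and decrements governs them. They are ambiguous, not contradictory. The missing tables do not prevent dispensing: at 70 kg the nearest-dose rule selects 90 mg for a 122.5 mg target and 360 mg for 5.25 × 70 = 367.5 mg. Several half-doses are also meant to be brief.

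The precedence argument does not fully answer the point. Neither passage says which prevails, and the sentence on deviations helps only if these rows are mandatory, which is not stated row by row. The row for UPCR above 0.5 is a direct decrease, so the restart argument does not reach it. The severe-rash row could be read as stopping at the last dose, but the final rise would then be 1.75 mg/kg/day, not the 3.5 that the row specifies.

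A reader might also infer that patients will often be affected, or that exposure data will be inconsistent. The documents support neither. The starting dose is 7 mg/kg/day, where the rules agree, and a conflict also needs a triggering event whose frequency is not given. The SAP (Study Treatment / Compliance) derives actual dose from recorded mg and current weight, and identifies reductions by a change of more than 15% in mg/kg, whichever rule a site followed.

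**Conclusion.** The point holds in limited form. The step rule and the direct 50% decrease for UPCR above 0.5 mg/mg contradict each other at 3.5 and 10.5 mg/kg/day and agree at 7 and 14. The severe-rash row is inconsistent with itself at the same two levels. The remaining restart-at-half-dose rows are unclear.

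Two of four counts dose levels, not patients. The conclusion assumes that the step rule applies to every safety reduction of a running dose, as its wording says. It does not require the 50% rows to be mandatory, since two instructions that differ need reconciling either way. No effect on the primary endpoint or on how exposure is computed is shown. This is an internal inconsistency in safety dosing that is worth correcting, not a flaw in the analysis. I take no view on which dosing rule is right.

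**What to change.** The sponsor should reconcile Protocol 6.1.1, the UPCR and rash rows of Table 6-2, and Appendix 14.1. The revised text should:

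1. State which rule takes precedence where a row gives a percentage.
2. State whether the step rule covers restarts after interruption.
3. Make every required reduction and re-escalation achievable from each of the four dose levels, including the return to the last dose after severe rash.
4. Say how a half-dose is rounded, including whether it is half of the mg/kg level or of the dispensed mg, and what happens when rounding leaves the dose unchanged or falls midway.
5. Label each row as recommended or mandated.

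The clinical content is for the sponsor to decide. The cost is wording in the next protocol amendment and a notice to sites. Sample size, endpoints and SAP derivations need no change on this account.

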6.1.2 Ancillary treatments

Not applicable

6.1.3 Rescue medication

Not applicable

6.1.4 Guidelines for continuation of treatment

Not applicable

6.1.5 Treatment duration

The total duration of treatment for each patient is up to 24 months (104 weeks). The total duration of the study for each patient is approximately 26 months (4-week Screening, 104-week Treatment, and 30-day Safety Follow-up).

6.2 Dose escalation guidelines

Not applicable

6.3 Dose modifications

6.3.1 Dose modification and dose delay

For patients who do not tolerate the protocol-specified dosing schedule, dose interruptions and/or reductions are either recommended or mandated in order to allow patients to continue the study treatment of defension FCT.

These dose modifications are summarized in Table 6-2. Deviations from the mandatory dose interruptions and/or reductions are not allowed. Permanent treatment discontinuation of deferasirox FCT is mandatory for specific events indicated in Table 6-2 or listed in Section 7.1.5.

These dose changes must be recorded on the Dosage Administration Record eCRF. It is important to keep an accurate dose adjustment records to enable an adequate evaluation of exposure.

Phlebotomy will be conducted at a frequency determined by the treating physician's clinical judgement for optimal iron control. The name of the facility, the date of phlebotomy, hematocrit level prior to phlebotomy and amount of blood withdrawn must be captured in Phlebotomy Record and local lab eCRFs. Phlebotomy must be interrupted when SF $\leq 100 \mu g/L$ and may be resumed when SF $\geq 100 \mu g/L$.

Novartis Amended Protocol Version 01 (Clean)

Table 6-2 Criteria for dose reduction / interruption and re-initiation of deferasirox FCT

Dose modifications for ICL670F2203		
Serum Ferritin (SF)		
After an initial starting dose (7 mg/kg/day) for 3 months (12 weeks), dose may be adjusted based on SF level. Dose increase cannot be more than 3.5 mg/kg/day at each adjustment.		
<300 µg/L	Decrease to 3.5 mg/kg/day	
300-1000 μg/L	Maintain 7 mg/kg/day	
>1000-2000 µg/L	Increase to 10.5 mg/kg/day	
>2000 µg/L	Increase to 14 mg/kg/day (higher doses are not allowed.)	
SF ≤ 100 μg/L at any time	Interrupt deferasirox FCT	
SF \geq 300 µg/L after dose interruption	Re-initiate deferasirox FCT 3.5 mg/kg/day. If SF continues to increase, increase to 7 mg/kg/day (maximum dose for maintenance phase).	
Body Weight		
Increase/decrease if weight changes >10% compared to baseline weight or weight at last dose adjustment due to a change in weight	Dose of study medication will be adapted using Dosing Table (provided in Appendix 14.1) When weight changes >10% compared to baseline weight or weight at last dose adjustment due to a change in weight, re-calculate dose. Smaller variations in weight (<10%) do not require dose adjustments.	
Investigations (Renal)		
Serum creatinine		
Single increase	Maintain dose and repeat assessment at next visit.	
Increased creatinine ≥ 33% from baseline (average of 2 samples) resulting in creatinine > ULN x 2 consecutive samples (at least 2 weeks apart)	Decrease by 7 mg/kg/day or interrupt if already at 7 mg/kg/day or lower.	
If dose is decreased, but increasing creatinine > ULN	Interrupt treatment.	
After interruption, if creatinine returns to within normal limits on 2 consecutive visits.	Resume 50% of the most recent dose prior to interruption. If after another 4 weeks, creatinine remains stable, resume 100% dose (adjust for weight if needed).	
Creatinine clearance > 40 and < 60 mL/min	Caution in patients if there are additional risk factors that may impair renal function, such as concomitant medications, dehydration, or severe infection.	

Dece medifications for ICL 67052202	
Creatinine clearance < 40 mL/min	Deferasirox must be discontinued.
or increased serum creatinine > 2x age-appropriate ULN	
Urine protein/creatinine ratio	
Any proteinuria	If new or worsening pre-existing proteinuria (assessed by dipstick), collect a urine sample for assessment by the central/local laboratory.
	In case of a single increase of the urinary protein/creatinine ratio, repeat the assessment at the next visit.
> 0.5 urine protein/ creatinine ratio (mg/mg) in two consecutive non-first void urine samples (a minimum of 48h apart), if all other causes of proteinuria have been	Decrease deferasirox by 50%. If UPCR resolves (< 0.5mg/mg) at the next study visit, resume 100% dose.
excluded.	
> 1.0 (mg/mg) in two consecutive non-first void urine	Interrupt deferasirox FCT.
samples (a minimum of 48h apart)	If the increased UPCR resolves (< 0.5 mg/mg) at the next study visit, resume dose at 50% of the last dose. If UPCR remains within normal limits after 4 weeks at the 50% reduced dose, resume study medication at 100% of the last dose.
Persistent proteinuria	If proteinuria persists, discontinue study treatment if the investigator believes it is in the best interest of the patient.
	Novartis may be contacted by the investigator to discuss dosing options.
	Dose adjustment must be based on central/local laboratory results.
Investigations (Hepatic)	
Isolated direct (conjugated) Bilirubin elevation	
> ULN – 1.5 x ULN	Maintain dose
> 1.5 - 3.0 x ULN	Interrupt dosing. Monitor LFTs ^a weekly or more frequently if clinically indicated until resolved to \leq 1.5 x ULN: If resolved \leq 14 days, then maintain dose.
	If resolved > 14 days, then \downarrow 1 dose level (3.5 mg/kg/day FCT)
> 3.0 - 10.0 x ULN*	Interrupt dosing. Monitor LFTs ^a weekly or more frequently if clinically indicated until resolved $\leq 1.5 \times \text{ULN}$:
	If resolved \leq 14 days, then \downarrow 1 dose level (3.5 mg/kg/day FCT)
	If resolved > 14 days, then discontinue patient from study drug. The patient must be monitored weekly (including LFTs ^a), or more frequently if clinically indicated until total bilirubin resolves to baseline or stabilizes over 4 weeks.

-		ا م الل ما م
しの	ntiae	entiai

Dose modifications for ICL670F2203	
> 10.0 x ULN*	Discontinue patient from study drug
	The patient must be monitored weekly (including LFTs ^a) or more frequently if clinically indicated until total bilirubin resolves to baseline or stabilizes over 4 weeks.
Isolated AST or ALT elevation	
> ULN - 3.0 x ULN	Maintain dose
> 3.0 - 5.0 x ULN	
For patients with baseline ≤ 3.0 x ULN	Maintain dose. Repeat LFTs ^a as soon as possible, preferably within 48-72 hours from awareness of abnormal results. If abnormal lab values are confirmed upon a repeat test, then monitor LFTs ^a weekly or more frequently if clinically indicated until resolves $\leq 3.0 \times ULN$.
For patients with baseline > 3.0 - 5.0 x ULN	Maintain dose
> 5.0 - 10.0 x ULN	
For patients with baseline $\leq 3.0 \times \text{ULN}$	Omit dose. Repeat LFTs ^a as soon as possible, preferably within 48-72 hours from awareness of abnormal results. Monitor LFTs ^a weekly or more frequently if clinically indicated until resolves \leq 3.0 x ULN.
	If resolved ≤ 14 days, maintain dose.
	If resolved > 14 days, ↓ 1 dose level (3.5 mg/kg/day FCT).
Baseline > 3.0 -5.0 x ULN	Maintain dose. Repeat LFTs ^a as soon as possible, preferably within 48-72 hours from awareness of abnormal results. If abnormal lab values are confirmed upon a repeat test, then monitor LFTs ^a weekly, or more frequently if clinically indicated until resolved to $\leq 5.0 \times ULN$.
> 10.0 - 20.0 x ULN	Omit dose. Repeat LFTs ^a as soon as possible, preferably within 48-72 hours from awareness of abnormal
	results. Monitor LFTs ^a weekly, or more frequently if clinically indicated until resolved to ≤ baseline, then↓ 1 dose level (3.5 mg/kg/day FCT).
> 20.0 x ULN	Discontinue patient from study drug.
	Repeat LFTs ^a as soon as possible, preferably within 48-72 hours from awareness of abnormal results. Monitor LFTs ^a weekly or more frequently if clinically indicated until resolved to baseline or stabilization over 4 weeks.
Combined ^b AST or ALT and total bilirubin elevations	
Normal baseline ALT and AST and total bilirubin:	
AST or ALT > 3.0 x ULN with total bilirubin > 2.0 x ULN without evidence of cholestasis ^c OR	Permanently discontinue deferasirox.

Novartis	
Amended Protocol Version 01 (Clean))

Dose modifications for ICL670F2203		
In patients with elevated baseline AST or ALT or total bilirubin:	Repeat as soon as possible, preferably within 48 hours from awareness of abnormal results. Monitor LFTs ^a weekly or more frequently if clinically indicated until AST, ALT, or bilirubin resolve to baseline or stabilize	
[AST or ALT > 2x baseline AND > 3.0 x ULN] OR	over 4 weeks. Refer to Section 6.3.3.1 for additional follow-up evaluations as applicable.	
[AST or ALT > 8.0 x ULN], combined with [total bilirubin > 2x baseline AND > 2.0 x ULN]		
Hepatic Impairment		
Moderate hepatic impairment (Child-Pugh Class B)	Interrupt deferasirox and monitor patient. If liver disease prognosis improves, re-start deferasirox 7 mg/kg/day FCT or 50% of previous dose, whichever is less. Increase dose 3.5 mg/kg/day FCT every 2 weeks to a maximum of 50% of previous dose if the investigator determines that the dose increase is in the best interest of the patient.	
Severe hepatic impairment (Child-Pugh Class C)	Discontinue deferasirox.	
Skin and subcutaneous tissue disorders		
Severe skin reaction		
Severe skin reactions, including Stevens-Johnson	Deferasirox must be immediately discontinued and not reintroduced	
syndrome (SJS) and Toxic epidermal necrosis (TEN)		
Drug reaction with eosinophilia and systemic symptoms (DRESS)		
Skin rash (other than SJS)		
Mild/moderate severity (minimal symptoms which require no or minimal supportive treatment)	Continue study drug without dose adjustment. If the rash persists >1 week or becomes more severe, interrupt dosing. After the rash resolves, resume study drug at 50% of last dose. If the rash does not recur, increase dose to	
	100% of dose after 2 weeks.	
Severe rash (distressing symptoms requiring	Interrupt treatment until resolution of rash.	
interruption of study medication and/or systemic steroids)	After the rash resolves, resume at 50% dose. If necessary, a brief course of oral steroids may be given concurrently with resumption of study drug. If the rash does not recur, increase in steps of 3.5 mg/kg/day for deferasirox FCT every 2 weeks until last dose is achieved. If the rash recurs, discontinue study treatment.	
Other adverse events		
Dose modification criteria for auditory and ocular disturbances		
Auditory (decreased hearing) and ocular (lens opacities)	Auditory and ophthalmic testing (including funduscopy) is required before starting deferasirox.	
disturbances have been reported with deferasirox.	If disturbances are noted, consider reducing the dose or interruption. Repeat testing may be done per investigator's judgement.	

Dose modifications for ICL670F2203		
Dose modification criteria for hypersensitivity reactions		
Cases of serious hypersensitivity reactions, such as anaphylaxis and angioedema, have been reported in patients receiving deferasirox. In the majority of cases, onset of the reaction occurred within the first month of treatment.	If reactions are severe, discontinue deferasirox and institute appropriate medical intervention. Due to the risk of anaphylactic shock, do not reintroduce deferasirox in patients who have experienced previous hypersensitivity reactions.	
Dose modification criteria for cytopenias		
Unexpected Cytopenias	Post-marketing reports (both spontaneous and from clinical trials) of cytopenias occurred mostly in patients with pre-existing hematological disorders and were frequently associated with bone marrow failure. Their relationship with deferasirox was uncertain. The standard clinical management of such hematological disorders is regular monitoring of complete blood count. Consider interrupting deferasirox for unexplained cytopenia. Consider reintroducing deferasirox once the cause of cytopenia is identified.	
Gastrointestinal disturbances		
Diarrhea, constipation, nausea, vomiting and abdominal pain.	At the first sign of diarrhea**, consider an anti-diarrheal medication, such as loperamide. Discontinue any laxative or stool softener and eat small, frequent meals.	
	If appropriate, maintain adequate hydration with approximately 8 glasses of water per day. If the gastrointestinal issues (diarrhea, constipation, nausea, vomiting and abdominal pain) persist, discontinue study drug if the investigator believes that is in the best interest of the patient.	
All dose modifications should be based on the worst preceding toxicity.		
a. Core LFTs consist of ALT, AST, GGT, total bilirubin (fractionated [direct and indirect] if total bilirubin > 2.0 x ULN), and alkaline phosphatase (fractionated [quantification of isoforms], if alkaline phosphatase > 2.0 x ULN.)		
"Combined" defined as total bilirubin increase to the defined threshold concurrently with ALI/ASI increase to the defined threshold		

If combined elevations of AST or ALT and total bilirubin do not meet the defined thresholds, please follow the instructions for isolated elevation of total bilirubin and isolated elevation of AST/ALT, and take conservative action based on the degree of the elevations (e.g. discontinue treatment at the situation when omit dose is needed for one parameter and discontinue treatment is required for another parameter). After all elevations resolve to the defined thresholds that allow treatment re-initiation, restart treatment either at the same dose or at one dose lower if criterion is met for dose reduction.

^{c.} "Cholestasis" defined as alkaline phosphatase elevation (> 2.0 x ULN and R < 2) in patients.

* Note: If total bilirubin > 3.0 x ULN is due to the indirect (non-conjugated) component only, and hemolysis as the etiology has been ruled out as per institutional guidelines (e.g., review of peripheral blood smear and haptoglobin determination), then \downarrow 1 dose and continue treatment at the discretion of the investigator.

** Note: anti-diarrheal medication is recommended at the first sign of abdominal cramping, loose stools or overt diarrhea.
